participants referred to this clinic already have expressed interest in receiving psychotherapy; and, thus, none of the 15 invited participants refused to participate in treatment. All participants were diagnosed with multiple comorbid depressive/anxiety disorders and reported severe, pre-treatment symptoms of anxiety and depression. PTSD was the most common presenting problem (46.6% PTSD, 26.7% SOC, 26.7% PD, 7.1%) and MDD was the most common comorbid disorder (64.2% MDD, 14.3% SOC, 7.1% PTSD, 7.1% PD). In general, participants were stabilized on multiple psychotropic medications prior to beginning CBT. Twelve of the fifteen participants finished treatment (80.0%). Treatment completers attended an average of 11.5, 50-minute sessions. As presented in the table below, participants demonstrated significant improvements in symptoms of impairment/quality of life, depression, stress, anxiety, and PTSD across all disorders and comorbidities. These findings provide preliminary support for the feasibility of a structured, transdiagnostic CBT protocol for the depressive/anxiety disorders among VAMC patients.

Scale (n)	Pre	Post	t (p)	Effect Size
IIRS-Impairment (12)	66.0 (14.9)	41.2 (19.8)	6.4 (< .001)	1.42
PTSD Checklist (7)	56.1 (13.1)	37.0 (14.0)	5.6 (< .01)	1.41
DASS-Depression (12)	26.2 (10.8)	10.3 (10.3)	5.3 (< .001)	1.51
DASS-Anxiety (12)	25.2 (10.7)	11.8 (9.1)	5.5 (< .001)	1.35
DASS-Stress (12)	26.3 (10.8)	15.7 (9.6)	3.6 (< .01)	1.04

Efficacy of Initial Transdiagnostic CBT in VAMC Patients

Note. Sum scores reported as means (standard deviations). Cohen's ds used for effect sizes.

Focus Group with OEF/OIF Veterans

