The results from the initial demonstration and OEF/OIEF Veteran focus groups were used to inform the revisions of the transdiagnostic CBT protocol. Once the revised protocol was complete, a demonstration of the revised transdiagnostic CBT protocol was initiated, once again, within standard clinical psychotherapeutic practices at the VAMC. The methods of the second demonstration were largely identical to the first demonstration. Thirty-one VAMC patients were recruited to complete the treatment. All participants were diagnosed with multiple comorbid depressive/anxiety disorders and reported severe pre-treatment symptoms. Among the twenty-three treatment completers, PTSD was the most common principal diagnoses (39.1% PTSD, 26.1% MDD, 21.7% PD, 8.7% SOC, and 4.3% OCD) and MDD was the most common comorbidity (43.5% MDD, 26.1% PTSD, 8.7% drug/alcohol abuse, 4.3% PD, 4.3% SOC). Treatment completers attended an average of 11.8, 45-60 minute sessions. As presented in the table below, participants demonstrated significant improvements in symptoms of impairment/quality of life, depression, stress, anxiety, and PTSD across all disorders and comorbidities. These findings provide additional support for the feasibility and likely efficacy of the transdiagnostic CBT protocol for the depressive/anxiety disorders among VAMC patients.

Efficacy of Revised Transdiagnostic CBT in VAMC Patients

Scale (n)	Pre	Post	t (p)	Effect Size
IIRS-Impairment (23)	64.3 (13.1)	37.3 (17.6)	7.3 (<.001)	1.74
PTSD Checklist (22)	56.5 (17.8)	33.7 (14.2)	7.2 (< .001)	1.42
DASS-Depression (23)	12.0 (6.1)	4.8 (4.3)	6.7 (< .001)	1.36
DASS-Anxiety (23)	10.9 (5.4)	5.0 (3.5)	6.2 (< .001)	1.30
DASS-Stress (23)	13.8 (5.1)	7.0 (3.9)	6.1 (< .001)	1.50

Note. Sum scores reported as means (standard deviations). Cohen's ds used for effect sizes.

D. RESEARCH DESIGN AND METHODS

Project Timeline

Project Component	Year	Timeframe
Preparing for RCT	Y01	month 01 – 06
Hiring staff	Y01	month 01 – 03
Training on procedures/protocols	Y01	month 03 – 06
Advertising upcoming trial for recruitment	Y01	month 03 – 06
Randomized controlled trial	Y01-Y04	month 06 – 54
Recruitment and active treatment		month 06 – 45
Ongoing data entry and integrity/fidelity review	VS	month 09 – 42
Data analyses of post-treatment (follow-up)		month 24 – 54
Grant application(s) (e.g., DVA CSR&D Merit)	Y04-Y05	month 36 – 60
Dissemination of findings	Y05	month 54 – 60
Revision of manual based on findings/feedback	Y05	month 54 – 60

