RCT of Transdiagnostic CBT

Objective

To evaluate the transdiagnostic CBT in a RCT of VAMC patients with depressive/anxiety disorders by investigating its preliminary efficacy in reducing symptomatology, comorbidity, and improving quality of life compared to BAT (psychotherapy control condition) at immediate post-treatment and 6-month follow-up. Patient satisfaction and predictors of feasibility (attendance and dropout) also will be assessed.

Recruitment Strategy

VAMC patients will be recruited through the Primary Care – Mental Health Integration program and CBT Clinic at the RHJ VAMC. Within these programs, all VAMC patients reporting symptoms of depression and anxiety meet with a mental health staff member to complete a diagnostic interview and self-report measures as part of their standard clinical practices. If VAMC patients endorse symptoms consistent with a depressive/anxiety disorder, the patient's interest in participating in research will be assessed and, if agreeable to research, patients will be put in contact with research staff (same day meeting and/or follow-up phone to schedule research assessment). A research assessment will be completed with the project staff to first complete consent documentation and then assess inclusion/exclusion criteria (with a targeted sample of 96 VAMC patients; \geq 72 completers), including a semi-structured clinical interview and self-report questionnaires focused on the psychiatric symptoms and quality of life (described later). Participants who meet diagnostic criteria for the targeted disorders will be randomized into a study condition, and will be assigned to a project therapist. Because most VAMC patients who meet study criteria likely will present with multiple depressive/anxiety disorders, principal diagnosis, or the most impairing of

the diagnosable disorders, will be used to select patients for participation. To balance diagnoses across the two conditions, a stratified random assignment based on principal diagnosis will be used for the most common principal diagnoses (MDD, PTSD, and PD). Based on new patient consults at the RJH VAMC (i.e., nearly 1000 in 2011 with at least one-half presenting with symptoms of an depressive/anxiety disorder), it is expected that \geq 50% of the recruited VAMC patients will have served in OEF/OIF and \geq 33% will be representative of minority groups.

Eligibility Criteria

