~33	6-Month Follow-Up Assessment	Clinical interview, immediate treatment interview, & self-report battery (7 measures), treatment satisfaction

Note. Behavior therapy involves the introduction, teaching, in-session and between-session practice, and mastery of behavioral therapeutic techniques designed to improve symptoms of depression and anxiety, including behavioral activation (BAT group) as well as situational, physical, thought, and emotional exposures (transdiagnostic CBT group). Final treatment session will take place between sessions 12-16, as determined by provider and participants' collective decision. Final treatment session will involve relapse prevention content. Post-treatment assessment will be completed 1 week immediately after final treatment session. 6-month follow-up assessment will be completed 6-months after final treatment session.

Randomization Procedures

Participants will be randomly assigned (1:1) to one of the two study arms (*n* = 48 per arm) using a permuted block randomization procedure. Randomization will be stratified by principal diagnostic group and block size will be varied to minimize the likelihood of unmasking. After determining eligibility and completing consent and baseline assessment materials, enrolled participants will be assigned to treatment groups by the Project Research Assistant using a computer generated randomization scheme. Once a participant is randomized and attends the first session, they will be included in the intent-to-treat analysis. Randomization will occur at the participant level. As such, we will take the following steps to minimize contamination between the two arms of the study: 1) only one member of a household will be eligible for enrollment; and 2) other VAMC providers will be informed of their patients' participation in the study, but will be blinded to the treatment condition of their patients.

Transdiagnostic CBT Treatment Condition

As noted above in the Preliminary Studies section, a transdiagnostic CBT protocol was developed and revised through two demonstration studies and one focus group. The resulting protocol involves several primary components, including psychoeducation on the symptoms of depression and anxiety (session 1), assessment of motivation and setup of treatment plans (session 2), exposure therapy (sessions 3-15), and relapse prevention (final session). In addition to these primary components, optional modules are included to supplement exposure

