In preliminary hypothesis testing, efficacy outcome variables will be compared using the generalized linear mixed models (GLMM) approach. This approach provides a general framework that accommodates a wide range of data types (continuous, ordinal, dichotomous, categorical, count) and distributional assumptions (e.g. Gaussian, Binomial, Poisson) and accommodates repeated measures, covariate structure among repeated observations, and missing data. In the first set of primary hypothesis testing analyses, immediate post-treatment scores for each outcome of interest will be used (separately) as the dependent variable in the model, intervention (transdiagnostic CBT versus BAT control) will be included as the primary independent variable, and pre-treatment scores for the outcome of interest will be added as covariates. When approximate normality is assumed, GLMM reduces to a general linear models (GLM) approach which, in the simplest case (intervention as the primary independent variable with baseline level of outcome variable as covariate), is equivalent to a comparison of change from baseline scores for transdiagnostic CBT versus BAT control using an independent sample t-test. Additional covariates (e.g. age, number of psychiatric comorbidities, race, sex, combat theatre, and number of treatment sessions) will be added to the model to adjust for putative confounding variables. If intervention differences in other baseline variables are found in initial descriptive analyses, these variables will be also be added to the multivariable model. In secondary analyses, the modeling procedure will be repeated for the period between immediate post-treatment and 6-month follow-up. Given that we are seeking preliminary evidence of treatment

efficacy (to justify the next step in this line of research), there will be no adjustment for multiple outcomes or time points to avoid an overly conservative approach at this preliminary stage.

Feasibility and Acceptability Analyses (Primary Aim 2)

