Measures of feasibility and acceptability are dropout proportions (dropout y/n), proportion of sessions attended, proportion of homework assignments completed, and patient satisfaction scores on the STTS-R. 95% CI for proportions will be used to estimate the proportion of participants who exit the study prematurely (drop out) within each intervention group and the difference in dropout proportions between the intervention groups. For the treatment satisfaction and adherence outcomes (STTS-R, proportion of missed sessions or homework assignments), the median and mean responses will be obtained within and between each intervention group. 95% CI for difference in means will be used to estimate the between intervention differences in treatment satisfaction (mean STTS-R) and adherence (e.g. average proportion of missed sessions or homework assignments) for the transdiagnostic CBT versus BAT control conditions. Frequency distributions describing the participants' reasons for noncompliance and discontinuation of participation will be developed.

The GLMM modeling framework described for Primary Aim 1 will be used to compare the effect of transdiagnostic CBT versus BAT control on treatment satisfaction, retention (dropout), and treatment adherence (% missed sessions, % homework completion). Dropout proportions (dichotomous outcome) and % of missed visits and % homework completion will be compared between the intervention groups using GLMM, with logistic/binomial regression analyses as special cases for dichotomous and percentage outcomes; STTS-R will be modeled as a continuous outcome using an appropriate link function. We also will model the longitudinal profile of adherence as a dichotomous outcome at each visit (e.g. attended/did not attend a given session). This will allow us to evaluate the trends in session attendance and to determine if the trends differ by intervention (e.g. whether the probability of missing visits is less/greater at earlier or later time points).

Exploratory Analyses - Diagnostic Groups

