 - 5 Post-graduate work or graduate degree

- 6. What is your disability status?
 - 1 Not disabled (skipped to Question #7)
 - 2 Disabled (go to Question #6b)
- 6b. If disabled through the Department of Veteran Affairs, please list percent of service connection: _____%
- 6c. If disabled through the Department of Veteran Affairs, what type of disability are you connected for?
 - 1 Physical health (e.g., diabetes, back injury, knee injury)
 - 2 Mental health (e.g., PTSD, major depression, adjustment disorder)
 - 3 Both physical and mental health
- 7. Which of the categories best describes your total annual combined income from all sources?
 - 1 0 < \$20,000
 - 2 \$20,000 < \$40,000
 - 3 \$40,000 < \$60,000
 - 4 \$60,000 < \$80,000
 - 5 \$80,000 < \$100,000
 - 6 > \$100,000
- 8. Please circle which branch of the Armed Services that you participated in?
 - 1 Army
 - 2 Navy
 - 3 Air Force
 - 4 Marine Corps
 - 5 Coast Guard
- 9. Please circle all of the combat theaters that you were deployed?
 - 1 World War II
 - 2 Korea
 - 3 Vietnam
 - 4 Desert Storm/Shield (First Gulf War)
 - 5 OEF/OIF (Afghanistan/Iraq Wars)
 - 6 Other (Please list): _____
 - 7 None
- 10. Have you ever participated in combat (e.g., fired your weapon or fired upon)?
 - 1 Yes
 - 2 No

APPQ

Please rate, on the following scale, the amount of fear that you think you would experience in each of the situations listed below if they were to occur in the next week. Try to imagine yourself actually doing each activity and how you would feel.

Fear Scale:

056666	7		8	}					
No fear Slight Moderate Marked				Ext	ren	ne			
Fear Fear	Fea	ar					Fe	ar	
1. Talking to people	0	1	2	3	4	5	6	7	8
2. Going through a car wash	0	1	2	3	4	5	6	7	8
3. Playing a vigorous sport on a hot day	0	1	2	3	4	5	6	7	8
4. Blowing up an airbed guickly	0	1	2	3	4	5	6	7	8
5. Eating in front of others	0	1	2	3	4	5	6	7	8
6. Hiking on a hot day	0	1	2	3	4	5	6	7	8
7. Getting gas at a dentist	0	1	2	3	4	5	6	7	8
8. Interrupting a meeting	0	1	2	3	4	5	6	7	8
9. Giving a speech	0	1	2	3	4	5	6	7	8
10. Exercising vigorously alone	0	1	2	3	4	5	6	7	8
11. Going long distances from home alone	0	1	2	3	4	5	6	7	8
12. Introducing yourself to groups	0	1	2	3	4	5	6	7	8
13. Walking alone in isolated areas	0	1	2	3	4	5	6	7	8
14. Driving on highways	0	1	2	3	4	5	6	7	8
15. Wearing striking clothes	0	1	2	3	4	5	6	7	8
16. Possibility of getting lost	0	1	2	3	4	5	6	7	8
17. Drinking a strong cup of coffee	0	1	2	3	4	5	6	7	8

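### The dropout comparison should not be adjusted for number of treatment sessions, which is measured after randomisation and nearly restates dropout; the other Aim 1 covariates should not be carried over either.

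*Combined protocol and SAP*

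**What the plan says.** Under Feasibility and Acceptability Analyses (Primary Aim 2), the plan first gives 95% confidence intervals for the dropout proportion in each arm and for the difference between arms. It then adds a model-based comparison: "The GLMM modeling framework described for Primary Aim 1 will be used to compare the effect of transdiagnostic CBT versus BAT control" on satisfaction, dropout and adherence, with logistic or binomial regression for dichotomous and percentage outcomes. No covariates are listed for Aim 2.

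The framework referred to is in the Primary Aim 1 analysis section: "Additional covariates (e.g. age, number of psychiatric comorbidities, race, sex, combat theatre, and number of treatment sessions) will be added to the model". Any other baseline variable found to differ between arms is added as well. The Procedures section separately makes the number of sessions a covariate in the outcome analyses, and the Missing Data section counts the dropout proportion among the outcome measures of feasibility.

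The Recruitment Strategy plans "with a targeted sample of 96 VAMC patients" and at least "72 completers". The notes to the visit table place the final session between sessions 12 and 16.

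**The concern.** Read together, these sections adjust dropout for how many sessions a person attended. That number is not a baseline characteristic: it is produced by staying or leaving, and the arm may affect it. Holding it fixed compares the arms among people who attended equally long, which is not the question in Hypothesis 2. It also gives the logistic model a predictor that may sort dropouts from finishers perfectly. Attendance has the same difficulty, since session count is part of what that outcome measures.

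A secondary matter is model size. Race and combat theatre have many levels (the theatre item reads "Please circle all of the combat theaters that you were deployed" and offers seven options), while few dropouts are expected.

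Dropout is a named element of Hypothesis 2. The plan does not say whether the difference in proportions or the model decides the comparison, so a failed or very imprecise model would leave covariates to be chosen after the data are seen.

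**Working it through.** **Expected number of dropouts.** The plan states neither a dropout count nor a power calculation. Its targets give 96 − 72 = 24 as a ceiling (25%). The pilots in Preliminary Studies had attrition of 3/15 = 20.0% and 8/31 = 25.8%, pooled 11/46 = 23.9%. Applied to 96, these give 19.2, 24.8 and 23.0. So about 24 is reasonable if dropout means not completing treatment.

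**Parameters.** Arm plus the six named covariates, one term each, is 7 parameters: 24/7 = 3.4 events per parameter. With race (six options, 5 terms) and theatre (seven options, 6 terms) fully coded, the count is 5 + 5 + 6 = 16: 24/16 = 1.5. Without session count the figures are 24/6 = 4.0 and 24/15 = 1.6.

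**Unadjusted benchmark.** Assume 9/48 against 15/48 dropouts (the split is an assumption).
- Difference: 18.75% − 31.25% = −12.5 points. Half-width: 1.96 × √[(0.1875×0.8125 + 0.3125×0.6875)/48] = 17.1 points.
- Odds ratio: (9/39)/(15/33) = 0.51. Standard error of its log: √(1/9 + 1/39 + 1/15 + 1/33) = 0.483. 95% CI: 0.20 to 1.31.
- Power: about 29%.

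**Simulation.** Each trial had 48 per arm and about 24 expected dropouts, fitted by maximum-likelihood logistic regression. There were 3,000 trials per setting, or 1,000 where session count was included. Baseline covariates had no true effect. The five baseline covariates were coded either as single terms (6 parameters with arm) or with race at four levels and theatre at six (12 parameters).

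*With session count, true odds ratio 0.51:*

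| Assumed sessions | Model | SD of arm log OR | Log OR inflation | Rejection rate |
|---|---|---|---|---|
| – | Arm only | 0.51 | 4% | 29% |
| Dropouts 1–11, finishers 12–16 | Any | no estimate in 100% of trials | – | – |
| Dropouts 1–14, finishers 10–16 | Arm + sessions | 0.76 | 0% | 13% |
| same | + 5 baseline terms | 0.96 | 19% | 15% |
| same | + multi-level race, theatre | 1.30 | 42% | 15% |

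In the overlap settings the arm coefficient was obtained in about 99% of trials or more. Sessions were drawn from dropout status alone, so these rows measure lost precision and small-sample inflation. They do not measure any attenuation from adjusting for something the arm itself affects.

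*Without session count:*

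| Model | True OR 0.51: mean OR (log OR inflation) | True OR 0.24: mean OR (log OR inflation) | False-positive rate, OR 1 |
|---|---|---|---|
| Arm only | 0.49 (4%) | 0.23 (3%) | 5.0% |
| 6 parameters | 0.47 (10%) | 0.20 (12%) | 5.7% |
| 12 parameters | 0.46 (16%) | 0.17 (22%) | 6.1% |

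Mean ORs are geometric. Coverage was 94–95% in the adjusted models. With 12 parameters some coefficient diverged in about 73% of trials, but the arm coefficient was still obtained in at least 99.8%.

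*Firth penalisation, five baseline terms:* mean OR 0.506 against a true 0.508, estimable in every trial, false-positive rate 3.7%.

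**The case against.** The carry-over is inferred. Aim 2 borrows a modelling framework, which may mean only the ability to handle different outcome types. The Aim 1 covariates are introduced as examples in a paragraph on efficacy, and that model's central covariate, the baseline score of the outcome, does not exist for dropout. This stands in part. Carry-over is the natural reading rather than an explicit instruction, but for session count the Procedures section supports it independently and nothing exempts dropout.

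Complete separation also depends on what counts as a dropout. The plan speaks of leaving the study prematurely, and the study ends at the 6-month follow-up. A person could finish treatment and then be lost, or stop treatment early and still attend assessments. Pilot completers averaged 11.5 and 11.8 sessions, so some finished with fewer than 12. This stands: overlap is plausible, and the 100% failure is one scenario. Overlap leaves a model that can be fitted but is much less precise.

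A reader might infer that about 24 events by themselves make the odds ratio unusable. The figures do not support that. Without session count the inflation is small against a standard deviation of about 0.6, there is no systematic bias when the arms are equal, and the diverging coefficients are for covariates rather than the arm. Nor does the plan require full coding of race and theatre: the enrolment table has only three non-zero racial categories.

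A reader might also infer that Aim 2 has no sound dropout estimate. It has one: the planned interval for the difference in proportions is untouched by any of this.

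**Conclusion.** The concern holds for number of treatment sessions. On the natural reading, the plan adjusts dropout for a post-randomisation variable that nearly restates it. The result is either no maximum-likelihood estimate (all dropouts below 12 sessions) or an arm log odds ratio whose standard deviation rises from about 0.5 to about 0.8–1.3, with power at a true odds ratio of 0.51 falling from about 29% to 13–15%. More events would not cure this.

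The remaining Aim 1 covariates are a secondary matter. They inflate a true log odds ratio by about 10–22%, against 3–4% with arm alone, while the false-positive rate stays near 6% and the odds ratio remains estimable.

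The split of dropouts between arms, the covariate distributions and the session-count overlap are assumptions, because the documents do not give them. The number of events also depends on how dropout is defined and on which intent-to-treat set is used: the Randomization Procedures require attendance at the first session, whereas the Missing Data section includes everyone randomised.

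**What to change.** In the Primary Aim 2 analysis section, and where the Procedures section makes session number a covariate, state that number of treatment sessions is not a covariate in the dropout or attendance models. State also that the Aim 1 covariate list is not carried over to dropout.

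Name the planned between-arm difference in dropout proportions, with its 95% CI, as the main dropout comparison, stratified by the randomisation strata (for example, a Mantel-Haenszel risk difference). If an adjusted model is also reported, limit it to one or two pre-specified baseline covariates with Firth penalisation. Define the dropout event in the same paragraph.

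This changes wording only, and the analysis becomes simpler. What is given up is a fully adjusted dropout odds ratio. Firth estimation was slightly conservative in the simulation.

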This study is designed to evaluate a transdiagnostic CBT specifically constructed to treat Veterans with depressive/anxiety disorders. The protocol includes both a primary transdiagnostic exposure component as well as supplementary disorder-specific modules to address ancillary symptoms. This transdiagnostic CBT has been investigated through focus groups with Veterans and two pilot demonstrations. This study will compare transdiagnostic CBT to an existing evidence-based version of CBT, behavioral activation therapy (BAT; psychotherapy control condition). A randomized controlled trial (RCT) of 96 DVA patients with depressive/anxiety disorders will be conducted to examine its efficacy, feasibility, and accessibility. Diagnostic interviews and self-

report symptom questionnaires will be completed at pre-treatment, immediate post-treatment, and 6-month followup assessment time points.

Research Primary Aim 1: To examine efficacy of transdiagnostic CBT on reducing transdiagnostic and disorderspecific mental health symptoms and improving quality of life at immediate post-treatment and 6-month follow-up. Hypothesis 1: The transdiagnostic CBT will result in significantly greater reductions in symptomatology (for principal and comorbid diagnoses) and improvements in quality of life compared to the BAT control condition at immediate post-treatment and 6-month follow-up. Although limited specific symptoms may ultimately be comparable across treatments (e.g., depression), the transdiagnostic CBT will demonstrate significantly greater reductions in the majority of symptoms (e.g., anxiety, panic, fear, stress).

Research Primary Aim 2: To examine feasibility and acceptability of transdiagnostic CBT

Hypothesis 2: The transdiagnostic CBT will be well tolerated by DVA patients as demonstrated by improved attendance and dropout rates, patient satisfaction questionnaires, and positive feedback in post-treatment patient interviews as compared to the BAT control condition. This hypothesis is based on the predicted greater symptom improvement (hypothesis 1) as well as the flexibility and individual tailoring of the treatment approach incorporated within transdiagnostic CBT.

B. BACKGROUND AND SIGNIFICANCE

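### The binomial regression named for % missed sessions and % homework completion has no term for differences between patients, so its standard errors are wrong unless one is added

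*Combined protocol and SAP*

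**What the plan says.** Section D, Feasibility and Acceptability Analyses (Primary Aim 2), lists four measures: dropout, proportion of sessions attended, proportion of homework completed, and STTS-R satisfaction. It treats attendance and homework in three ways.

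- **Estimation.** "95% CI for difference in means will be used to estimate the between intervention differences in treatment satisfaction (mean STTS-R) and adherence", where adherence means each patient's proportion of missed sessions or homework, averaged within arm.
- **Arm comparison.** "The GLMM modeling framework described for Primary Aim 1 will be used to compare the effect of transdiagnostic CBT versus BAT control". Dropout, % missed visits and % homework completion are compared "using GLMM, with logistic/binomial regression analyses as special cases for dichotomous and percentage outcomes".
- **Visit level.** "We also will model the longitudinal profile of adherence as a dichotomous outcome at each visit", to see whether attendance trends differ by arm.

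The framework referred to is in the Primary Aim 1 efficacy section, which says that it "accommodates repeated measures, covariate structure among repeated observations, and missing data". That section specifies no random effect or correlation structure. It illustrates a special case with the Gaussian model, which reduces to an ordinary general linear model.

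Hypothesis 2 in Specific Aims rests tolerability in part on attendance: "as demonstrated by improved attendance and dropout rates".

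**The concern.** Plain binomial regression fixes the variance of a patient's miss count at n·p(1−p), where n is that patient's number of sessions. This holds only if sessions are independent and every patient in an arm has the same miss probability. Someone who stops treatment misses all remaining sessions together, and patients are likely to differ in homework habits. Both make the true variance larger than the model allows.

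If instead each patient's percentage is entered as a single 0–1 value without its denominator, the model assumes a variance of p(1−p) per patient. That is far too large, so the test almost never rejects.

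Attendance and homework are two of the four Aim 2 measures. A model-based test with the wrong standard error could report an attendance difference that is not there, or miss one that is. It could also disagree with the plan's own confidence interval on the same data.

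**Working it through.** The documents give no error rate, miss rate or within-patient correlation for adherence, so there is no stated figure to reproduce.

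**Inputs from the documents**
- 48 patients per arm, 1:1 (Randomization Procedures).
- 12–16 sessions (Procedures).
- Non-completion: "with a targeted sample of 96 VAMC patients" with at least 72 completers (Recruitment Strategy), so up to 24/96 = 25%.
- Pilots (Preliminary Studies): 12 of 15 finished, so 3/15 = 20% did not. For the second, "Thirty-one VAMC patients were recruited to complete the treatment" and 23 completed, so 8/31 = 26% did not.

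**Assumptions**
- Two-sided 0.05, matching the 95% intervals, because no test level is stated.
- 10–20% of sessions missed apart from dropout.
- 10–25% dropout, with the last session attended before dropout (L) uniform on 1 to m−1.
- Where used, an intraclass correlation (ICC) of 0.1–0.2.

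**Formula.** If the true variance is φ times the binomial variance, the actual error is 2·[1 − Φ(1.96/√φ)].

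**Case 1: counts, sessions after dropout counted as missed, no other heterogeneity.** Take m = 12, dropout 25%, miss rate b = 10%.
- Completer: mean 12 × 0.1 = 1.2; variance 12 × 0.1 × 0.9 = 1.08.
- Dropout: L has mean 6 and variance (11² − 1)/12 = 10. Misses have mean 12 − 0.9 × 6 = 6.6 and variance 0.09 × 6 + 0.81 × 10 = 8.64.
- Overall mean: 0.75 × 1.2 + 0.25 × 6.6 = 2.55, so p = 2.55/12 = 0.2125.
- Overall variance: 0.75 × (1.08 + 1.44) + 0.25 × (8.64 + 43.56) − 2.55² = 8.44.
- Binomial variance: 12 × 0.2125 × 0.7875 = 2.01. So φ = 8.44/2.01 = 4.20.
- Error: 2·[1 − Φ(1.96/2.05)] = 34%. Simulation gave 33–34%.

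The same steps at the ends of the range:

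| Sessions | Dropout | Miss rate | φ | Error |
|---|---|---|---|---|
| 12 | 10% | 20% | 4.54/2.19 = 2.07 | 17% |
| 12 | 25% | 10% | 4.20 | 34% |
| 16 | 10% | 20% | 7.31/2.92 = 2.51 | 22% |
| 16 | 25% | 10% | 14.76/2.68 = 5.51 | 40% |

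**Case 2: counts, only sessions before dropout.** Here φ ≈ 1 + (m − 1)·ICC.
- m = 12: ICC 0.1 gives φ = 2.1 and 17.6%; ICC 0.2 gives φ = 3.2 and 27.3%.
- m = 16: ICC 0.1 gives φ = 2.5 and 21.5%; ICC 0.2 gives φ = 4.0 and 32.7%.
- ICC 0 gives φ = 1 and 5%.

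Simulation with dropout gave about 16–32% over this ICC range. Dropouts contribute fewer sessions, which lowers φ a little.

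**Case 3: unweighted percentages.** For the worked example, the true variance of a patient's proportion is 8.44/144 = 0.0586. The model assumes 0.2125 × 0.7875 = 0.167. The ratio is 0.35, so the error is 2·[1 − Φ(1.96/√0.35)] = 0.09%. Across settings it was about 0–0.1%.

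**Alternatives, same null simulations.** Pearson-scaled binomial and the Welch t-test on patient proportions stayed at about 4–6%. A random-intercept logistic model gave 5.2–5.8% for the arm effect with 20–25% dropout (500 trials). Under beta-binomial data without dropout (400 trials per setting, so imprecise) it gave about 4–5% at ICC 0.1–0.2 and 9–13% at ICC 0.4.

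**The case against.** The strongest reply is that the plan says GLMM, inside a framework described as handling repeated measures. A GLMM with a patient random intercept is a legitimate reading and largely removes the problem for the overall comparison. This stands. A reader might infer that the plan prescribes a test with a known, inflated false-positive rate. The text does not support that: it permits independent sessions, unweighted percentages or a patient effect, and these err in different directions or hardly at all. What remains is that the one model named for percentage outcomes has no patient term, and the plan does not commit to adding one.

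Second, the size depends on figures outside the documents. Miss rates, ICC and dropout timing are assumed. The plan does not say that sessions after dropout count as missed. Course length is settled jointly between 12 and 16 sessions, so a dropout has no fixed denominator, and dropout is already a separate outcome. This also stands, and is why both ways of counting are shown.

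Third, the planned interval for the difference in mean patient proportions is valid, hypothesis testing is described as preliminary, and Hypothesis 2 also draws on dropout, satisfaction and interviews. This limits the damage but does not repair the model-based comparison.

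A reader might also infer that the visit-by-visit model will produce false arm-by-time trends. That would require a random intercept alone with dropouts coded as misses, and the plan specifies neither. The supportable statement is that this model must account for within-patient correlation.

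**Conclusion.** The point holds in conditional form. Taken literally, the named special case gives standard errors that are too small on session counts and too large on unweighted percentages. At nominal 5% with 48 per arm, the null rejection rate on counts is about 17–40% if sessions after dropout count as missed, with no other heterogeneity. It is about 16–32% at ICC 0.1–0.2 if they do not, and 5% only if patients do not differ. On unweighted percentages it is about 0–0.1%. All of these rest on the assumed miss rates, dropout timing and ICC listed above. The documents supply the arm size, the session range and the 25% non-completion ceiling.

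Only % missed sessions and % homework completion are affected. Dropout (one yes/no per patient), STTS-R and the planned interval for mean proportions are not. The change should be made before analysis, since the choice of model alone can decide whether an attendance difference is reported.

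**What to change.** In the Primary Aim 2 analysis section, replace binomial regression for % missed sessions and % homework completion with one of these:

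- a linear model on each patient's proportion with a Welch or robust standard error, which matches the planned interval for the difference in means; or
- binomial regression on counts with the session or homework denominator, plus either an estimated dispersion or a patient random intercept.

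State whether sessions after dropout count as missed, and with what denominator. For the visit-by-visit attendance model, state how within-patient correlation is handled, for example with patient-clustered standard errors. Ordinary logistic regression can stay for dropout.

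The cost is a sentence or two of wording and a different model option, with no new data. Standard errors will be wider than under plain binomial regression on counts: by √φ, so about √2 = 1.4 to √5.5 = 2.3 times at dispersion 2–5.5. Nominally significant attendance differences will be rarer.
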